Center for Anti-Infective Research and Development  
Hartford Hospital

Protocol

Original Version Date: May 12, 2020  
Amendment 1 Version Date: July 7, 2021

**Pharmacokinetics of Imipenem/Cilastatin/Relebactam in Critically Ill Patients Receiving  
Extracorporeal Membrane Oxygenation (ECMO)**

NCT04493151

Principal Investigator: [name], FIDP, FCCP  
Center for Anti-Infective Research and Development  
Hartford Hospital  
[name]  
[name]  
[contact]  
[contact]  
Email: [[contact]](mailto:[contact])

Section #2- Core Protocol	
2.1 Objectives & Hypotheses	
1.0 PROTOCOL AMENDMENT 1: July 7, 2021
 
 
1. Section 2.5 exclusion criteria #5 modified to remove valproic acid.
 
2. Section 2.5 addition of criteria #6 excluding patients currently receiving or anticipated to receive valproic acid. The change in criteria 5 and 6 will allow for patients to receive imipenem-cilastatin-relebactam despite a prior recent history of valproic acid use.
 
3. Section 2.5 screening/baseline: removal of urine analysis with microscopy due to unnecessary test not relating to patient safety.
 
 
2.0 OBJECTIVES
 
 
1. To determine the pharmacokinetics of imipenem and relebactam in critically ill adult patients supported by ECMO
 
 
2.1.1 HYPOTHESES
 
 
1. Imipenem and relebactam pharmacokinetics in critically ill patients receiving ECMO support will be consistent with parameters previously defined in critically ill adult patients not supported by ECMO
 

2.2 Background & Rationale, Significance of Selected Topic & Preliminary Data	
Extracorporeal membrane oxygenation (ECMO) is a mechanical circulatory support device used temporary in critically ill patients with heart and/or respiratory failure unresponsive to maximal conventional therapy. Briefly, ECMO is a form of cardiopulmonary life-support where blood is extracted from the vascular system (i.e., peripheral or central vein) and circulated by a mechanical pump while it is oxygenated and re-infused into the patient's circulation. ECMO can be used in two different configurations depending on the patient's requirement: veno-venous (VV-ECMO) when only respiratory support is needed and veno-arterial (VA-ECMO) for cardiac and/or respiratory support (1). Although controversial until 2009, the clinical benefit of ECMO therapy was substantiated when the CESAR study, a multicenter, randomized controlled trial that included adult patients with respiratory failure, demonstrated an increased survival without disability at 6-month follow-up (2). Since then, ECMO has been increasingly used worldwide in pediatric and adult patients, and remarkable technological improvements (e.g., innovative device design, cannula, oxygenators) have been made, resulting in improved clinical outcomes (3).
 
At our large tertiary care trauma center, we perform VV-ECMO or VA-ECMO in an increasing number of critically ill adult patients each year (n=60 in 2019). With more adult patients receiving ECMO support, there is a need to understand how ECMO circuits affect the pharmacokinetics (PK) and disposition of drugs. ECMO is not a disease-modifying treatment, and its effectiveness relies on the effect of other interventions, such as antibiotics in patients with severe infections where optimal exposure is crucial for treatment success. It is well known that critically ill patients may experience alterations in antibiotic PK, and as a result, dosing modifications are generally required (4). Multiple in vitro and in vivo studies have shown that ECMO may further alter the PK of certain antibiotics by resulting in lower plasma concentrations unable to achieve pharmacodynamic thresholds (5). Intrinsic drug properties such as lipophilicity and protein binding appear to be predictive of this artificial loss, presumably due to drug adsorption and sequestration within the oxygenator circuit, increases in compensatory volume of distribution and even changes in total body clearance (6-9). However, these specific drug properties may


	
not always be predictive; a recent ex vivo study with ceftolozane observed 92% loss in the circuit over 24 hours even though this antibiotic is neither lipophilic nor highly protein bound (10). Other factors related with the ECMO circuit itself such as the type of pump and presence of oxygenator have been also associated with antibiotic loss (9,10). In contrast, some investigators largely conclude that antibiotic exposures are minimally altered by ECMO and thus antibiotic dosing should be consistent with critically ill patients not supported by ECMO (11-13). In light of this inconsistent data, the sequestration and clinical PK of individual antibiotics should be assessed to confirm optimal dosing in this patient population.
 
Imipenem/cilastatin/relebactam (Recarbrio®, Merck & Co, Inc, Kenilworth, NJ) is a novel carbapenem/β-lactamase inhibitor combination recently approved by the U.S. Food and Drug Administration (FDA). Imipenem/cilastatin/relebactam has enhanced activity against multidrug resistant Gram-negative bacteria, including imipenem resistant strains (14). As a result of its potent activity against multidrug-resistant pathogens, it is reasonable to surmise that imipenem/cilastatin/relebactam will be prescribed to treat serious infections in critically ill patients, including those who are supported on ECMO. Optimizing the dosing regimen in critically ill patients receiving ECMO will be paramount to achieving successful clinical response and minimizing the risk of resistance development. Both imipenem and relebactam have low protein binding (~20%) and low octanoal/partition coefficients (Log P: -3.8 to -0.86 and -3.1 to -1.1, respectively), which suggests that drug disposition should be minimally affected by ECMO (15-17). However, Jaruratanasirikul and colleagues compared imipenem PK parameters between 10 critically ill patients on ECMO and 18 similarly ill patients not supported by ECMO (18). They observed that ECMO, or the underlying physiological state produced by it, resulted in a significantly higher total volume of distribution (<math>33.4 \pm 13.9</math> L vs. <math>21.3 \pm 15.0</math> L) and significantly lower total body clearance (<math>10.0 \pm 10.5</math> L/h vs. <math>21.5 \pm 9.6</math> L/h). The authors suggest that these alterations may require dosing modifications (i.e., 1 g q6h) to maintain optimal pharmacodynamic exposure. It should be noted, however, that the PK parameters in the studied ECMO patients were within the range of imipenem PK values observed in other critically ill patients without ECMO, suggesting that the patients may not have been evenly matched for comparison (19). Moreover, there are currently no data evaluating the disposition of relebactam in patients supported by ECMO. We propose a clinical pharmacokinetic study to determine imipenem and relebactam exposure in critically ill patients supported by ECMO.

2.3 Study Design	
The study will be a prospective, open-label, single-center, phase 1b PK study of imipenem/cilastatin/relebactam in eight critically ill adult patients receiving ECMO support at Hartford Hospital. PK analyses will be conducted to assess exposure attainment in these eight ECMO patients.

2.4 Study Flowchart	
Not Applicable

2.5 Study Procedures	
Study Location This study will take place at Hartford Hospital, an 867 bed, tertiary care hospital in Hartford, CT. ECMO is prescribed in approximately 60 critically ill adult patients each year, split between use of VV-ECMO and VA-ECMO. We anticipate that the

	
majority of patients with sepsis who qualify for this study to be receiving VV-ECMO.
 
Study population
 
The study population will include eight critically ill adult patients (<math>\geq 18</math> years of age) receiving ECMO support in the medical or surgical intensive care units at Hartford Hospital. Patients with documented or presumed infection are eligible. Any patient with infection will be treated with standard antibiotics by the attending provider. To ensure representation of patients across the renal function spectrum to be included in the study, half of the enrolled patients will have a creatinine clearance <math>\geq 60</math> mL/min at screening and half will have a value between 15 and 59 mL/min.
 
Inclusion Criteria: Patients eligible to participate in the study must meet all of the following criteria prior to any study-related procedure:
 
 
• Age 18 years or older;
 
• On support with VV- or VA-ECMO;
 
• Documented infection or presumed infection as confirmed by the presence of at least one of the following criteria within the past 72 hours: 
 
◦ Documented fever (oral, rectal, tympanic, or core temperature <math>> 38.5^{\circ}</math> C)
 
◦ Hypothermia (oral, rectal, tympanic, or core temperature <math>< 35.0^{\circ}</math> C)
 
◦ An elevated white blood cell (WBC) count <math>\geq 12,000</math> cells/mm<math>^3</math>
 
 
 
 
Exclusion Criteria: Patients will be considered ineligible if they meet any of the following criteria:
 
 
• If female, currently pregnant or breast feeding;
 
• History of any moderate or severe hypersensitivity or allergic reaction to any <math>\beta</math>-lactam agent (a history of mild rash to a <math>\beta</math>-lactam followed by uneventful re-exposure is not a contraindication);
 
• Severe renal dysfunction defined as a creatinine clearance <math>< 15</math> mL/min (calculated by the Cockcroft-Gault equation using actual body weight) or requirement for continuous renal replacement therapy or hemodialysis;
 
• Hemoglobin less than 8 mg/dL at baseline;
 
• Use of probenecid or imipenem within 3 days before study drug infusion;
 
• Current use of valproic acid or anticipated use during study enrollment.
 
• Acute liver injury, defined as aspartate aminotransferase (AST) or alanine aminotransferase (ALT) <math>> 5</math> times the upper limit of normal, or AST or ALT <math>> 3</math> times the upper limit of normal with an associated total bilirubin <math>> 2</math> times upper limit of normal;
 
• Any rapidly-progressing disease or immediately life-threatening illness (defined as imminent death within 48 hours in the opinion of the investigator);
 
• Any condition or circumstance that, in the opinion of the investigator, would compromise the safety of the patient or the quality of study data;
 
 
Planned or prior participation in any other interventional drug study within 30 days.
 
Study Procedures
 
Screening/Baseline
 
Screening/Baseline assessments and procedures must be completed within 24 hours before the start of the study drug infusion. Potential subjects who do not meet enrollment criteria may, as appropriate, repeat the screening assessments once at a later time for possible enrollment into the study. Local laboratory results will be used to determine subject eligibility for study enrollment. Any protocol-required eligibility laboratory evaluations already done as part of the patient's regular medical care within 24 hours before the start of the study drug infusion on Study Day 1 do not

--	--

	
have to be repeated for purposes of determining eligibility for this study.
 
 
• Obtain informed consent in writing from patient, legal authorized representative, or next of kin, according to local regulations.
 
• Clinical Assessments:
 
• Obtain a complete medical and surgical history, including: a) all active conditions and all conditions diagnosed within the previous 1 year
 
• Perform a complete physical examination (general/appearance; head, eyes, ears, nose, and throat [HEENT]; neurological; pulmonary; cardiovascular; gastrointestinal; musculoskeletal; and skin)
 
• Record height and weight
 
• Record resting pulse, blood pressure, and respiratory rate; oxygen saturation (by pulse oximeter), including rate of supplemental oxygen (i.e., FiO2); ventilator support; and highest (or lowest if hypothermia) daily temperature (oral, rectal, tympanic, or core) measured
 
• Record total fluid balance including total fluid intake and total fluid output for the period encompassing the signing of the ICF to the start of the study drug infusion
 
• Record each component of the Acute Physiology and Chronic Health Evaluation II (APACHE II) assessment at Screening/Baseline
 
• Record ECMO settings
 
• Record all prior medications taken or received within 3 days before study drug infusion
 
• Identify, assess, and record any new adverse events or Serious Adverse Events (SAE) after signing of informed consent
 
• Laboratory Assessments:
 
• Collect the following labs within 24 hours of study dose administration: serum creatinine, blood urea nitrogen, glucose, sodium, potassium, chloride, bicarbonate, albumin, total protein, complete blood count (CBC) with differential, total bilirubin, direct bilirubin, alkaline phosphate, alanine aminotransferase, and aspartate aminotransferase. A serum hCG test will be collected for females of child-bearing potential.
 
• Calculation of CrCL using Cockcroft-Gault based on screening/baseline serum creatinine:
 
 
Calculated CrCL = <math display="block">\frac{(140 - \text{age in years}) \times \text{ideal body weight (kg)}^{\text{a,b,c}}}{72 \times \text{Scr (mg/dL)}}</math>
 
Multiply by 0.85 for female patients
 
a Ideal body weight (IBW, kg): Males = 50 + [2.3 × (Height (in) - 60)]; Females = 45.5 + [2.3 × (Height (in) - 60)]
 
b For patients with total body weight (TBW) that is greater than 20% over IBW, use adjusted body weight (ABW, kg): IBW + 0.4*(TBW-IBW)
 
c If TBW is less than IBW, use TBW in equation
 
Imipenem/cilastatin/relebactam Administration
 
Imipenem/cilastatin/relebactam will be dosed according to current prescribing information based on creatinine clearance (20). Four to six doses of imipenem/cilastatin/relebactam, each infused over 0.5 hours, will be administered to achieve steady-state. The dose will be prepared according to manufacturer recommendations in precisely 100 ml of 0.9% sodium chloride. Imipenem/cilastatin/relebactam must be administered through a peripheral intravenous catheter, peripherally inserted central catheter, central line, or port-a-catheter, whichever is determined to be most appropriate by the local investigator and care provider for each participant. Participants will also receive standard intravenous antibiotic therapy (excluding generic or branded intravenous imipenem) to treat their suspected infection, as determined by the responsible provider. No

--	--

	
other intravenous medications will be co-administered with imipenem/cilastatin/relebactam.
 
Study Day 1
 
 
• Vital signs (temperature, heart rate, blood pressure, respiratory rate) will be recorded within 15 minutes prior to starting the study drug infusion.
 
• Participants will receive imipenem/cilastatin/relebactam as described above. Exact start and stop times will be recorded in military time.
 
• Identify, assess, and record any new adverse events or Serious Adverse Events (SAE)
 
• Concomitant medications will be recorded.
 
• Blood samples will be collected as described below.
 
 
Study Day 2
 
 
• Participants will receive imipenem/cilastatin/relebactam as described above. Exact start and stop times will be recorded in military time.
 
• Blood samples will be collected as described below.
 
• Concomitant medications will be recorded.
 
• Clinical Assessments:
 
• Perform a complete physical examination
 
• Record resting pulse, blood pressure, and respiratory rate; oxygen saturation (by pulse oximeter), including rate of supplemental oxygen (i.e., FiO2); ventilator support; and highest (or lowest if hypothermia) daily temperature (oral, rectal, tympanic, or core) measured
 
• Identify, assess, and record any new adverse events or SAE
 
• Laboratory Assessments:
 
• Collect the following labs within 24 hours after completion of last blood sample collection: serum creatinine, blood urea nitrogen, glucose, sodium, potassium, chloride, bicarbonate, albumin, total protein, complete blood count (CBC) with differential, total bilirubin, direct bilirubin, alkaline phosphate, alanine aminotransferase, aspartame aminotransferase, and urine analysis with microscopy.
 
 
Sample Collection
 
Blood samples (4 mL) will be collected in K2EDTA vacutainers before the first imipenem/cilastatin/relebactam dose (i.e., blank), and at 0.5 and 6 hours following the first dose, and then at 0, 0.5, 0.75, 1, 2, 4, 5, and 6 hours after the start of the final dose, when concentrations are expected to be at steady-state. All blood samples will be collected pre-oxygenator. Additionally, protein binding will be determined at the 0.5 hour time point of the final dose. The timing of all blood samples should be +/- 5 minutes of protocol defined time, except for the 0.5 hour (peak concentration), which can be +5 minutes the end of infusion and should be collected as close to the end of the infusion as possible.
 
Processing of clinical samples
 
Blood samples will be immediately stored on ice and centrifuged within 30 minutes of collection at 4° C and 1300 x g for 10 minutes to separate the plasma. Immediately after centrifugation, 1.0 mL of plasma from each sample will be transferred (using a 1.0 mL pipette) to a previously labeled cryovial containing 1.0 mL of plasma stabilizer (2-(N-morpholino) ethanesulfonic acid (MES)). A second 1.0 mL of plasma will be added to a second cryovial (labeled with stabilizer) to have a back-up sample. Thereafter, cryovials will be capped and inverted at least six times to mix the plasma with the stabilizer. The cryovials will be stored at -80° C until concentration determination. No more than 60 minutes should elapse between the blood draw and freezing of plasma sample.

--	---

	
Protein Binding determination
 
An additional 10ml blood sample will be collected for imipenem and relebactam protein binding determination at time points described above. Plasma will be separated by centrifugation as previously explained. Approximately 0.9 mL of plasma will be loaded in an ultrafiltration device (Centrifree®, Merck Millipore Ltd., Ireland) and centrifuged for 45 minutes at 10° C at 2,000 x g to obtain an ultrafiltrate containing only free-drug concentrations. Protein binding will be conducted in triplicate. The ultrafiltrate volume will be measured, transferred to a cryovial and then, an equal volume of the stabilizer will be added (confirmation of processing instructions for protein-free imipenem and relebactam will be provided by Q2 Solutions, Ithaca, NY). The cryovials will be stored at -80° C until concentration determination. The final protein percentage will be calculated by dividing the free concentration by the total plasma concentration and subtracting from 100 (%).

2.6 Study Duration
	
IRB Submission and Contracting: 2 months      Patient Enrollment: 8 months      Data Analyses: 2 months      Final Report: 2 months


2.7 Statistical Analysis and Sample Size Justification
	
Data Collection
 
Patient demographics, medical/surgical history, concomitant medications, and adverse event data will be collected throughout the study on a provided case report form. Protected Health Information (PHI) will be maintained at CAIRD.
 
Imipenem and Relebactam Concentration Determination
 
Cryovials containing plasma and protein free filtrate will be overnight shipped on dry ice to Q2 Solutions (Ithaca, NY) for imipenem and relebactam concentration determination. The back-up vial will be shipped separately. Imipenem and relebactam concentrations will be determined by a liquid chromatography mass spectrometry assay.
 
Pharmacokinetic Analyses
 
Non-compartmental
 
Non-compartmental modeling will be conducted using WinNonlin (Pharsight Corporation, Cary, NC) using the latest version licensed for the laboratory. All concentration time curves will be plotted for visual inspection. The following pharmacokinetic parameters will be estimated for imipenem and relebactam in each of the 8 participants. The maximum concentration (<math>C_{max}</math>) will be the highest concentration observed for the concentration time profile of each participant. The time to maximum concentration (<math>T_{max}</math>) will be the observed sampling time of the <math>C_{max}</math>. The minimum concentration (<math>C_{min}</math>) will be the lowest concentration observed for the concentration time profile of each participant that occurs after the observed <math>C_{max}</math>. Lambda (<math>\lambda_z</math>) will be the resulting slope of the regression line of best fit. Half-life (<math>T_{1/2}</math>) will be calculated as <math>\ln(2)/\lambda_z</math>. Area under the curve for the dosing interval (<math>AUC_{0-\tau}</math>) will be calculated by the linear/log trapezoidal rule (linear during increasing concentrations, log during decreasing concentrations), where <math>\tau</math> is the dosing interval for the drug studied. The AUC to infinity (<math>AUC_{\infty}</math>) will be calculated as the AUC extrapolated to infinity by the equation: <math>AUC + C_{last}/\lambda_z</math>. Clearance (CL) will be estimated by Dose/<math>AUC_{0-\tau}</math>. The volume of distribution based on the terminal elimination phase (<math>V_z</math>) will be estimated by Dose/<math>(\lambda_z * AUC_{0-\tau})</math>.
 
Population Pharmacokinetic Analyses
 
Imipenem and relebactam concentrations will be co-modeled using the non-parametric adaptive grid program (NPAG) with adaptive gamma in the Pmetrics


	
package for R (Laboratory of Applied Pharmacokinetics and Bioinformatics, Los Angeles, CA) using either a one or two compartment model. Appropriate model selection will be based on visual inspection, observed versus predicted plots, and Akaike Information Criterion (AIC). The effect of specific body size descriptors (actual body weight, ideal body weight, body mass index, body surface area), calculated CrCL, and ECMO flow rate will be analyzed for correlation with pharmacokinetic parameters (i.e., CL and volume of distribution). By including a similar proportion of participants with creatinine clearance above and below 60 ml/min, a variable range of clearance values will be represented in the population analyses.
 
Pharmacodynamic Analysis
 
The free imipenem and relebactam concentration of each of the eight participants will be assessed for free time above the MIC (<math>fT > MIC</math>, applied for imipenem) and free area under the curve to MIC (<math>fAUC/MIC</math>, applied for relebactam) exposure using the imipenem susceptibility breakpoint of 2 <math>\mu</math>g/mL for Pseudomonas aeruginosa.
 
Sample Size
 
No target sample size is provided statistically as this will be a descriptive and exploratory study. Therefore, this study will enroll eight critically ill adult patients on ECMO support based primarily on empirical considerations and feasibility. This number is considered sufficient to meet the study objectives.

2.8 Specific Drug Supply Requirements	
Recarbrio® (Imipenem/cilastatin/relebactam) 1.25g vials (n=50 vials)

2.9 Adverse Experience Reporting	
Safety and Adverse Event Monitoring
 
Participants will be monitored for any sign or symptom of adverse events (AE) throughout the course of the study. Unanticipated, life-threatening or fatal adverse events will be reported to the IRB, the manufacturer, and the Food and Drug Administration according to federal guidelines. All adverse events requiring medical attention will be treated by the study physician and will be recorded by the investigator. For the purpose of this study, an adverse event will be defined as any pathologic or unintended change in the structure (signs), function (symptoms), or chemistry (laboratory values) of the body associated with the use of the study drug, whether or not considered drug related, and will be categorized as one of the following:
 
 
• MILD – present, but easily tolerated
 
• MODERATE – discomfort that interferes with usual activities
 
• SEVERE – incapacitating, inability to work or do usual activities
 
 
Relationship of the AE to the study medication (i.e., causality) will be evaluated according to the investigator's opinion, as one of the following:
 
 
• Concurrent condition – unrelated to study drug
 
• REMOTE adverse drug event – little or no temporal relationship to study drug
 
• POSSIBLE adverse drug event – temporal relationship to study drug
 
• PROBABLE adverse drug event – commonly associated with study drug
 
• DEFINITE adverse drug event – reappeared on re-challenge of study drug
 
 
All SAEs will be reported to the Institutional Review Board, sponsor, and the Food

	and Drug Administration according to Federal and local guidelines. A serious adverse event will be defined as any adverse event that results in death, is immediately life-threatening, requires or prolongs hospitalization, or is an important medical event that may jeopardize the participant or may require medical intervention to prevent one of the previously mentioned outcomes.
2.10 Itemized Study Budget	See Proposed Budget

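### The only non-compartmental volume planned is Vz, which under two-compartment kinetics rises with clearance at unchanged distribution; Vss should be added and volume conclusions tied to it and to the population model.

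*Combined protocol and SAP*

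**What the plan says.** The non-compartmental paragraph of section 2.7 lists Cmax, Tmax, Cmin, λz, half-life, AUC0-τ, AUC∞, CL and a single volume, Vz: "The volume of distribution based on the terminal elimination phase". CL is Dose/AUC0-τ and Vz is Dose/(λz × AUC0-τ), so Vz = CL/λz. λz "will be the resulting slope of the regression line of best fit"; the points entering the fit are not stated. No AUMC, MRT or Vss is listed.

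The population analysis in the same section fits a one- or two-compartment model and relates its CL and volume to body size, CrCL and ECMO flow. The section does not say which volume the study's conclusions will rest on.

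Three other places bear on the point.

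- The hypothesis (2.1.1) is that the pharmacokinetics "will be consistent with parameters previously defined in critically ill adult patients not supported by ECMO". It names no volume type, reference value or margin.
- The background (2.2) describes a published imipenem comparison in which ECMO "resulted in a significantly higher total volume of distribution" (33.4 against 21.3 L) together with a lower clearance (10.0 against 21.5 L/h). It adds that the groups may not have been evenly matched.
- Section 2.5 enrols half the patients at CrCL 15–59 mL/min and half at 60 or above. The stated reason: "To ensure representation of patients across the renal function spectrum to be included in the study".

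**The concern.** Vz is a pure distribution volume only in a one-compartment system. With a peripheral compartment, λz reflects both elimination and return from tissue. When CL rises, λz rises less than in proportion, so CL/λz goes up. Vz is close to Vss when CL is low relative to exchange and exceeds it increasingly as CL rises. This is a property of the quantity and is present with noise-free data; it is separate from how precisely λz can be estimated.

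The study will contain a wide range of CL, and its hypothesis invites comparison with published values from patients whose CL may differ. Differences in Vz between patients, or from a published figure, could then be taken for fluid or circuit effects when they are partly clearance effects. A real volume difference could also be flattened. In a descriptive study of eight patients the reported parameters are the result, so the choice of volume matters for interpretation.

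**Working it through.** **Plan's own figures.** The plan states no calculation for volume. The cited contrasts are 33.4/21.3 = 1.57 for volume and 10.0/21.5 = 0.47 for CL, ECMO over non-ECMO.

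**Inputs from the protocol.** 0.5 h infusion; final-dose samples at 0, 0.5, 0.75, 1, 2, 4, 5 and 6 h; AUC linear when rising and logarithmic when falling; Vz = CL/λz; CL values of 10 and 21.5 L/h from section 2.2.

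**Assumed, not in the documents.** τ = 6 h; dose 500 mg (it cancels from Vz and Vss under linear kinetics); V1 = V2 = 15 L, so true total volume is 30 L; Q = 5, 10 or 20 L/h; λz from the best-fitting set of the last 3 to 6 points.

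**Step 1: exact algebra.** Vz = CL/β, where β is the smaller root of x² − (CL/V1 + Q/V1 + Q/V2)x + (CL/V1)(Q/V2) = 0. At Q = 10:

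- CL 10: β = [2.000 − √(4.000 − 1.778)]/2 = 0.2546, so Vz = 10/0.2546 = 39.3 L.
- CL 21.5: β = [2.767 − √(7.654 − 3.822)]/2 = 0.4045, so Vz = 21.5/0.4045 = 53.2 L.

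The ratio is 1.35 with distribution unchanged. The same algebra gives 1.17 at Q = 20 and 1.62 at Q = 5.

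**Step 2: the planned calculation on noise-free steady-state profiles.** Vss = CL × MRT, with MRT = (AUMC0-τ + τ × Clast/λz)/AUC0-τ − 0.25 h.

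| Q (L/h) | Vz at CL 10 → 21.5 (L) | Ratio | Vss at CL 10 → 21.5 (L) | Ratio |
|---|---|---|---|---|
| 20 | 34.4 → 41.0 | 1.19 | 30.6 → 32.6 | 1.07 |
| 10 | 38.6 → 53.6 | 1.39 | 30.1 → 32.4 | 1.08 |
| 5 | 40.9 → 77.4 | 1.89 | 27.6 → 31.8 | 1.15 |

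At Q = 5 part of the 89% arises because the 6 h window does not reach the true terminal phase at CL 10 (fitted λz 0.243, exact β 0.195). The clearance dependence alone is the 62% of step 1.

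**Step 3: one compartment.** With true V = 21.3 L, planned Vz reads 21.4 L at CL 10 and 21.7 L at CL 21.5. There is no meaningful artefact.

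**Step 4: direction in the cited comparison.** Take the cited volumes as true Vss with V1 = V2: 33.4 L at CL 10 (ECMO) and 21.3 L at CL 21.5 (non-ECMO), true ratio 1.57.

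| Q (L/h) | Vz ratio, ECMO/non-ECMO | Vss ratio |
|---|---|---|
| 5 | 42.2/60.3 = 0.70 | 29.6/24.7 ≈ 1.19 |
| 10 | 42.4/39.1 = 1.08 | 33.1/24.6 = 1.35 |
| 20 | 38.2/29.8 = 1.28 | 33.9/24.6 = 1.38 |

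Vz shrinks, removes or reverses the increase. Vss attenuates it but keeps the direction.

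**Step 5: when the artefact reaches 1.57.** With Vss fixed at 21.3 L and CL moved from 10 to 21.5, exact Vz rises by 1.57 or more only if Q is at or below 7.6 L/h (V1/Vss = 0.3), 5.7 (0.5) or 2.5 (0.8).

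**The case against.** The strongest reply has five parts.

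1. **The size is conditional.** The documents give no Q, V1 or V2 and leave one versus two compartments open. This stands, and it is why a range is given.

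2. **A reader might infer that Vz could manufacture an ECMO volume increase as large as the one cited.** The documents do not support this. At Q = 10 the rise over the cited clearances is 39%, below 57%. CL was also lower on ECMO in that comparison, so the artefact inflates the non-ECMO side. For example, with V1 = 12, V2 = 9 and Q = 10, Vz reads 34.4 L, close to the cited ECMO volume, but only at CL 21.5, the non-ECMO clearance. At CL 10 it reads 25.9 L. A false increase on ECMO would need higher CL than in the reference group.

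3. **A reader might infer that the protocol sets out to test 33.4 against 21.3 L.** It does not. That contrast is background, its volume type is unstated, and there is no comparator arm, margin or planned comparison of Vz between renal strata.

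4. **The population model also estimates volume, and the covariate analysis is placed there.** This is correct and limits the damage. But no sentence says that volume conclusions rest on the model, and Vz is to be estimated for every participant.

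5. **Vss is imperfect.** Also correct. With 10% assay noise, Q = 10 and true 30 L, median Vss was 25, 28 and 32 L at CL 5, 10 and 21.5, against 25, 32 and 49 L for Vz. At CL 10 the two are equally far from the truth. From CL 10 to 21.5, Vss rises 32/28 = 1.14 and Vz 49/32 = 1.53.

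It is also true that Vss could be computed afterwards from the same samples. Specifying it now avoids choosing the volume after seeing the data.

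**Conclusion.** The point holds as a moderate matter of reporting and interpretation. If kinetics are two-compartment, the only planned non-compartmental volume mixes clearance with distribution in a study where clearance is deliberately spread. Over CL 10 to 21.5 L/h, with an assumed V1 = V2 = 15 L, the false change in Vz is about 20% to 89% for Q from 20 down to 5 L/h, against about 7% to 15% for Vss. With faster exchange it is smaller, and with one compartment it is negligible.

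For a comparison like the one cited, the likely consequence is masking of a true volume increase. The documents do not support the reading that the plan would produce a spurious ECMO effect. CL, AUC, fT>MIC and fAUC/MIC do not use Vz and are not affected.

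**What to change.** In section 2.7:

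- Add Vss = CL × MRT from the final-dose profile, with the steady-state term (τ × Clast/λz) and the subtraction of half the infusion time.
- State that conclusions about volume rest on Vss and on the population-model volume (V1 + V2 if two-compartment).
- State that comparisons are made only with published volumes of the same type. The type of the 33.4 and 21.3 L figures should be established before they are used.
- Keep Vz as a listed descriptive value.

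The cost is a few sentences and one more parameter to report, with no extra samples or patients. Vss keeps some error from sparse early sampling, λz and assay noise: in the noise-free runs at Q = 5 it read 26 to 32 L for a true 30 L over CL 5 to 21.5. It should therefore be read alongside the model estimate.
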